### For surgeons:

The research coordinator will establish a private meeting with each surgical team member involved in the study who will be performing the surgical repair for a mandible fracture. The research coordinator will bring the necessary consent forms for the surgeon's review.

During this appointment the study coordinator will introduce the Likert scale questions that the surgeon will be responsible for answering post- operatively if they are selected to use the 3D model for that procedure. That way if the surgeon elects to remove themselves from the study, they may do so at that present time. If the surgeon agrees to the Likert scale questions, the study coordinator will begin the consenting process.

During the consenting process the research team member will go over all the details and timelines for the study. Contact information will also be provided so if any questions or concerns arise, they can contact the study team.

The study team will ensure that the surgeon is by no way obligated to participate in this study. The procedure and normal post operative standards of care will be provided if the

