**1.2 Describe the hypotheses to be tested.**

The investigators will test the hypothesis that patients randomized to the intervention (3D printing with pre-bent plate) arm have less operative room time and less time for the critical part of the procedure than patients in the control arm (no 3D printing, current standards of care). Personalized medicine and care for fracture treatment.

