## TEMPLATE: RESEARCH PROTOCOL

NUMBER	ACTIVE DATE	PAGE
HRP-503	02-04-2020	5 of 35

	
3D printing is a technology that allows for physical creation of a 3D model (usually made of plastic) based on computer generated 3D images from CT scans. The 3D images of craniofacial skeleton using computer software are routinely generated and, in turn, these 3D images can be used to create a plastic 3D model using a 3D printer. Unstable or comminuted facial fractures need to be reduced and rigidly fixated using titanium plates and screws. Bending and shaping of the plates is usually performed by free hand based on the surgeon's estimation of what best fits the fracture. Often, bending the titanium plates to the shape of pre-injury skeletal contour is difficult when the bone is fractured into many pieces or is unstable, or when the patient is edentulous (missing several teeth). The process can increase the time spent in surgery and the bent plates may not snugly fit the fracture. For these difficult cases, one option is to use commercially manufactured 3D printed patient-specific models. The patient-specific models provide the benefit of correct shape/form for increased surgical accuracy and decreased intra-operative time. Thus, redefining standards of care increasing surgical satisfaction from the surgeon and patient, while decreasing the time in the OR.

	
3.1 Describe the resources available to conduct the research. Justify the feasibility of recruiting the required number of suitable subjects within the agreed recruitment period, e.g. how many potential subjects do you have access to? What percentage of those potential subjects do you need to recruit?
 
The study will be conducted at University of Cincinnati Medical Center which is designated as the region's only Level I trauma center by the American College of Surgeons. This will be a joint study with the divisions of Oral and Maxillofacial surgery, Plastics and Reconstructive surgery and Otolaryngology who are designated as the primary teams for management of all facial trauma at the institution. Thousands of consults are requested annually through UCMC ED and neighboring hospital systems for these specific injuries.

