	
6.1 Thoroughly describe the study design.
 
We plan to conduct a randomized controlled trial on trauma patients brought to either UCMC or UC HH OMS for treatment of isolated mandibular fractures. This study plans to elucidate whether the utilization of 3D models during operations where effective in minimizing both OR time and operational costs. Subjects will be identified based off the initial physical assessments made by surgical specialists from OMS, Plastic Surgery, and otolaryngology. Once the subjects are identified the research coordinator will conduct a screening of the patient to ensure they meet the inclusion/ exclusion criteria for the study and then randomize the patient into either normal standard of care for surgical repair of the fractured mandible or normal standard of care for surgical repair of the fractured mandible aided by a 3D printed model of the patient's jaw. Any chart reviewing will be conducted from existing electronic medical records maintained by UC Health EPIC and OMS Vision. All the following data would be based on the patient's condition at the time of surgery.

	
Following completion of the procedure, for the surgeons who received aide via the 3D model they will be asked to answer a brief Likert Scale survey outlining their thoughts how effectively or ineffectively the model assisted them. In addition to this information, if they feel the model increased efficiency saving time, they will be asked to state how much time they felt was saved. This time differential will be compared to current CPT codes for OR time to understand how much in operational costs were saved by utilizing the models.

6.0 PROCEDURES INVOLVED	

6.2 Detail the procedures being performed, specifically the interaction or intervention with human subjects and/or their identifiable information. Please be clear and concise and provide information relevant to the current study. For
	

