**TEMPLATE: RESEARCH PROTOCOL**

NUMBER	ACTIVE DATE	PAGE
HRP-503	02-04-2020	11 of 35

10.0 INCLUSION AND EXCLUSION CRITERIA & VULNERABLE POPULATIONS
	
10.1 Describe how subjects will be screened for eligibility.
 
The screening of potential participants will be performed by the providers of University of Cincinnati Medical Center's Department of Oral and Maxillofacial Surgery clinic located at Holmes Hospital (UCMC OMS HH clinic), or surgical providers from plastic surgery and otolaryngology located in UCMC including resident physicians, attending physicians, research staff, and clinic staff. Surgical team members from the division of plastic and otolaryngology will be consented and recruited to participate in this study by providing their feedback post operatively. The diagnosis and treatment planning will strictly be made by a resident or attending surgeon. However, an elected research coordinator will complete a standardized eligibility form on REDCap based on the study's inclusion/exclusion criteria to finalize participant selection
	
	
10.2 Describe/list the inclusion/exclusion criteria for the study.
 
Inclusion Criteria:
 
Patient ≥ 18 years of age
 
Patients who have received either a cone beam or conventional CT
 
Admitted through UCHMC emergency department
 
All isolated mandible fractures referred to UCH OMS
 
Surgical team members from the division of plastic and otolaryngology
 
Exclusion Criteria:
 
Patient < 18 years of age
 
Patients who have neither cone beam nor conventional CT
 
Patients requiring a repeat procedure
 
Unexpected exposure of hardware
	
	
10.3 Indicate specifically whether you will include each of the following vulnerable populations. Check all that apply. (You may not include members of the below populations as subjects in your research unless you indicate this in your inclusion criteria and are approved by the IRB to include them in your research) The member checklists are for reference only to ensure you provide appropriate safeguards and justification. The checklists do not need to be completed.
	

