**TEMPLATE: RESEARCH PROTOCOL**

NUMBER	ACTIVE DATE	PAGE
HRP-503	02-04-2020	12 of 35

	
of a pregnancy test are negative or until delivery.) (HRP-412 MEMBER CHECKLIST Pregnant Women)
 
 Non-Viable Neonates (HRP-413 – MEMBER CHECKLIST Non-Viable Neonates)
 
 Uncertain Viability Neonates (HRP-414 – MEMBER CHECKLIST Uncertain Viability Neonates)
 
 Prisoners (HRP-415 – MEMBER CHECKLIST Prisoners)
 
10.4 If the research involves individuals listed in 10.3 or other individuals who are vulnerable to coercion or undue influence, please justify based on the applicable checklist and describe additional safeguards included to protect their rights and welfare.
 
N/A
 
10.5 If the research involves or may involve individuals who are students or employees where the research is taking place, please describe additional safeguards included to protect their rights and welfare.
 
Not Applicable

	
11.1 Indicate the total number of subjects to be accrued.
 
We aim to obtain 50 procedures for each arm of the study (100 in total)
 
50: standard surgical procedures aided by use of 3D Printed model
 
50: procedures carried out by standard surgical repair for isolated mandibular fractures (No model)

	
11.2 If applicable, distinguish between the number of subjects who are expected to be enrolled and screened, and the number of subjects needed to complete the research procedures.
 
N/A

	
12.1 Describe when, where, and how potential subjects will be recruited.
 
Subjects of this study are those that require emergent medical attention and are referred to either UCHMS Emergency Department or to UC OMS for treatment. Subjects will be triaged by the clinical providers, and the research coordinator will then complete a standardized informative process. Regardless of involvement, the subject will undergo the same treatment course as any other patient presenting with an isolated mandibular fracture. For the consenting of the surgical team members, they will undergo a research presentation given by the research coordinator in which they have an adequate amount of time to ask any questions or concerns before deciding to be a part of the study.

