	
12.2 Describe the source of the subjects.
 
Subjects for the study are any patient are referred to HH OMS for treatment of isolated mandibular fracture. The referral arrives will need emergent medical treatment arriving from the emergency department. No subject will be sought after for the purposes of the study since the population will be emergent cases admit to UCHMC. Surgical team members will be

	
identified by both the PI and research coordinator for recruitment based off of past surgical collaboration on routine procedures at UCMC.
 
12.3 Describe the materials that will be used to recruit subjects. (Attach copies of these documents in the Recruitment section on the local site documents page in RAP. For advertisements, attach the final copy of printed advertisements (avoid making copies until approved in case modifications are required). When advertisements are taped for broadcast, attach the final audio/video tape. You may submit the wording of the advertisement prior to taping to preclude re-taping because of inappropriate wording, provided the IRB reviews the final audio/video tape)
 
N/A

13.0 COMPENSATION FOR SUBJECTS	
13.1 Describe the amount, method, and timing of payments to subjects.
 
N/A

14.0 WITHDRAWAL OF SUBJECTS	
14.1 Describe the anticipated circumstances under which subjects will be withdrawn by the study team from the research without their consent.
 
Given the strict inclusion and exclusion criteria of the study, we anticipate very few circumstances in which patients will need to withdraw by the study team without their consent.
 
14.2 Describe any procedures for orderly termination.
 
Patients will be withdrawn from the study if they unfortunately succumb to their injuries related to any polytrauma that caused the underlying mandibular fracture before any procedures can be completed. Surgeons who no longer wish to provide feedback via the Likert scale questions will also no longer be associated with the study.
 
14.3 Describe procedures that will be followed when subjects withdraw from the research, including partial withdrawal from procedures with continued data collection, withdrawal of previously collected data upon request, etc.
 
Patients and surgeons who are withdrawn from the study for the purposes listed earlier will be excluded from all study results.

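### Surgeon participation rests on a survey used only in the 3D arm and the operator is not fixed before randomisation, so operator choice and surgeon withdrawal can depend on the arm

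*Protocol*

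**What the plan says.** The tested hypothesis in section 1.2 is that patients in the 3D arm "have less operative room time and less time for the critical part of the procedure than patients in the control arm". Section 11.1 plans 50 procedures per arm. Operators may come from several services: "This will be a joint study with the divisions of Oral and Maxillofacial surgery, Plastics and Reconstructive surgery and Otolaryngology" (3.1).

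On surgeons as participants, section 10.1 says that members of the plastic surgery and otolaryngology teams "will be consented and recruited to participate in this study by providing their feedback post operatively". Section 6.1 limits that feedback to one arm: "for the surgeons who received aide via the 3D model they will be asked to answer a brief Likert Scale survey". Section 23.3 agrees. The coordinator meets every surgeon in the study who will repair a mandible fracture and presents the questions that the surgeon is "responsible for answering post- operatively if they are selected to use the 3D model for that procedure". A surgeon may decline at that meeting. Section 14.2 covers later withdrawal: "Surgeons who no longer wish to provide feedback via the Likert scale questions will also no longer be associated with the study". Section 14.3 then excludes withdrawn patients and surgeons from all results.

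On timing, section 6.1 has the coordinator screen the patient and "then randomize the patient into either normal standard of care for surgical repair of the fractured mandible" or the same care aided by the model. Section 9.2 places this at the evaluation, after the surgical provider's history and physical. Section 6.5 mentions a surgeon assigned to the case, but not when or by whom that assignment is made.

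**The concern.** Randomising patients balances what is settled before allocation. It does not balance an operator who is chosen, replaced or withdrawn after the arm is known. The operating surgeon can plausibly influence both total OR time and time for the critical part of the procedure. The only described burden on the surgeon falls on 3D cases, so the reason to decline or leave also arises in that arm. The protocol neither ties the patient to a consented surgeon before allocation nor says what happens to the randomised patients of a surgeon who leaves. The comparison exposed to this is the one in the trial's own hypothesis.

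**Working it through.** **Reading the sections together**

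1. Survey duty: 3D arm only (6.1, 23.3).
2. Surgeon participation: described as giving that feedback (10.1, 23.3; section 18.1 speaks of it in the same way).
3. Consequence of stopping the survey: the surgeon leaves the study (14.2) and is excluded from results (14.3).
4. Randomisation: at the evaluation (9.2).
5. Operator named or consented by that time: not required in 6.1, 9.2, 10.2 or 23.3. The patient criteria in 10.2 do not link a patient to a consented surgeon.

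Steps 1 to 3 make withdrawal of a surgeon depend on exposure to one arm. Steps 4 and 5 leave the choice of operator open after the arm is known. Section 14.3 does not say whether excluding a surgeon also excludes that surgeon's patients, which leaves two possibilities.

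- The cases are kept or reassigned to another surgeon. The operator mix may then differ between arms.
- The cases are dropped. Randomised patients then leave the analysis after allocation because of a survey used in one arm. If only 3D cases go, the remaining operator mix also differs. If the surgeon's cases go from both arms, the mix is better protected, but randomised patients and precision are still lost.

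**Illustrative size**

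The protocol states no alpha, power, effect size or standard deviation for OR time, so there is no figure to reproduce beyond 50 + 50 = 100, which agrees. The following shows scale only.

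Inputs: n = 50 per arm (11.1); two-sided alpha 0.05 (assumed); f, the difference between arms in the share of cases done by a given group of operators (assumed); s, the difference of that group's mean time from the other operators' mean, in SD units (assumed). The model takes a common SD and ignores clustering by surgeon.

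- SE of the difference in means = √(2/50) = 0.20 SD.
- Detectable difference at 80% power = (1.960 + 0.842) × 0.20 = 0.56 SD.
- Bias = f × s. Type I error = Φ(−1.96 + bias/SE) + Φ(−1.96 − bias/SE).

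| f | s (SD) | Bias (SD) | Bias/SE | Type I error |
|---|---|---|---|---|
| any | 0 | 0 | 0 | 5.0% |
| 0.1 | 0.5 | 0.05 | 0.25 | 5.7% |
| 0.2 | 0.5 | 0.10 | 0.50 | 7.9% |
| 0.3 | 0.5 | 0.15 | 0.75 | 11.7% |
| 0.3 | 1.0 | 0.30 | 1.50 | 32.3% |

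The sign is also unknown. If the over-represented control operators are slower, the bias favours the model; if they are faster, it runs against it.

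For loss of precision alone, if dropped cases left 40 per arm (assumed), the detectable difference would be 2.802 × √(2/40) = 0.63 SD instead of 0.56 SD.

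**The case against.** A reader might infer that surgeons who opt out go on to supply control cases only, so that OR time is confounded with operator. The protocol does not support that. Section 23.3 approaches every operating surgeon whatever the arm, and a surgeon who declines leaves the study, not just its 3D arm. Sections 14.2 and 14.3 take a withdrawing surgeon out of the study and its results. No section lets such a surgeon stay on for control cases. Confounding is possible; it is not established.

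A reader might also infer that the operator is picked after allocation, or that 3D cases are steered to surgeons who favour the model. The text does not say so. The phrase in 23.3 about being selected to use the model can equally mean that the surgeon's patient was randomised to it. Section 23.3 also has a surgeon present at the pre-operative consultation, and 9.2 has a surgical provider complete the examination before randomisation. That person may turn out to be the operator.

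These arguments remove the stronger claims and leave the gap. Nothing says that the person who examines the patient will operate, and silence on timing gives no protection. Section 3.4 calls the study blinded and speaks of withholding information from surgical providers, but a surgeon handed the model knows the arm. Section 14.3 removes surgeons from the results without saying what becomes of their patients.

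Adjustment for surgeon may be in a statistical analysis plan that is not at hand, and its absence here is not counted as a fault. It could reduce an imbalance between recorded operators. It would not restore dropped cases or separate arm from surgeon for anyone who operates in one arm only.

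**Conclusion.** The concern holds in a limited form. As written, a survey given in one arm can determine whether a surgeon stays in the study, the operator need not be named or consented before randomisation, and the fate of a withdrawn surgeon's randomised patients is not stated. Operator choice and surgeon withdrawal can therefore depend on the arm, and either route could bias the comparison of OR time.

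Size and direction cannot be derived from the protocol. The effect is nil if surgeons do not differ in time, if none withdraws, or if the operator is in practice settled beforehand. It is small under mild assumptions and serious only if both the difference in operator share and the difference in time are large. Every figure for f and s above is an assumption. The change should be made because it is cheap and closes both routes, not because bias has been shown.

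**What to change.** - In sections 9.2 and 10.2, require the responsible operating surgeon to be named on the REDCap eligibility form, and to have consented to the study, before the allocation is shown. Apply this to both arms. A patient whose named surgeon has not consented or has left is not randomised.
- Keep a log of any later change of operator, with its reason.
- In section 14.3, state that a surgeon's withdrawal from the survey removes only the survey data, and that every randomised patient's OR times are kept and analysed in the randomised arm. Bring the wording of 14.2 into line with this.

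The cost is one required form field, one eligibility line, a change log and a short edit to section 14. Some patients of non-participating surgeons will not be recruited, and rota changes must be recorded. Surgical care is unchanged.

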**TEMPLATE: RESEARCH PROTOCOL**

NUMBER	ACTIVE DATE	PAGE
HRP-503	02-04-2020	24 of 35

patient participates or not. There will be adequate time for the surgeon to ask any question or discuss any concerns.

Participants will be provided a consent for both to review and take with them during the meeting. The one copy the research team will obtain the signature of the participant and the research team member that obtained the consent. This form will be kept in the regulatory binder in the research coordinators office in a locked filing cabinet in a personal office where only the study team members have access to.

**23.4 Describe how consent of the subject will be documented in writing.**

Both the patients and surgeons will be provided a consent for both to review and take with them. The one copy the research team will obtain the signature of the participant and the research team member that obtained the consent. This form will be kept in the regulatory binder in the research coordinators office in a locked filing cabinet in a personal office where only the study team members have access to.

**23.5 Describe the conditions under which you believe it would be appropriate to obtain ongoing consent from the subjects.**

Ongoing consent and communication will be important throughout the study. The subject has the right to be removed from the study at any point in time. It is crucial that the subject's recovery and well-being be placed above determining effectiveness of the device. Subjects will be provided the research coordinators phone number and IRB contact information so they can report any issues if need be or any issues directly to the IRB if worried about notifying the study team directly.

24.0 WAIVER OF DOCUMENTATION OF CONSENT	
24.1 Justification for waiver of consent documentation. Check all that apply and provide rationale for all checked items. Please note that certain combinations of the selections below may justify a waiver of documentation. Please refer to HRP-411 – MEMBER CHECKLIST Waiver of IC Documentation to determine if your study qualifies for a waiver of documentation, and which boxes to check to justify the waiver.
 
 
 	N/A not requesting a waiver of documentation of consent.	
 
 	The research presents no more than minimal risk to subjects. Rationale/Explanation	
 
 	Written information describing the research is to be provided to the subject, subject parent(s) or guardian(s), or subject Legally Authorized Representative. Rationale/Explanation	
 
 	Written information describing the research does not need to be provided to the subject, subject parent(s) or guardian(s), or subject Legally Authorized Representative. Rationale/Explanation	
 
 	The research involves no procedures for which written consent is normally required outside of the research context. Rationale/Explanation	
 
 	The only record linking the subject and the research would be the consent documentation. Rationale/Explanation	
 
 	The principal risk of a signed consent document would be the potential harm resulting from a breach of confidentiality. Rationale/Explanation	
 
 	The subjects are members of a distinct cultural group or community in which signing forms is not the norm. Rationale/Explanation	
 
 	There is an appropriate alternative mechanism for documenting that informed consent was obtained. Rationale/Explanation	
 
 	The research is not FDA-Regulated. Rationale/Explanation	
 
 	The written script of the information to be provided orally, electronically, or on paper (information sheet) includes all required and appropriate additional elements of consent disclosure. When requesting a waiver of documentation, an information sheet is required. This box should always be checked for a waiver of documentation. (Follow HRP-502I TEMPLATE Information Sheet) Rationale/Explanation	
 
 	Other Describe any other reasons/explanations for request of waiver/alteration	
 
			N/A not requesting a waiver of documentation of consent.		The research presents no more than minimal risk to subjects. Rationale/Explanation		Written information describing the research is to be provided to the subject, subject parent(s) or guardian(s), or subject Legally Authorized Representative. Rationale/Explanation		Written information describing the research does not need to be provided to the subject, subject parent(s) or guardian(s), or subject Legally Authorized Representative. Rationale/Explanation		The research involves no procedures for which written consent is normally required outside of the research context. Rationale/Explanation		The only record linking the subject and the research would be the consent documentation. Rationale/Explanation		The principal risk of a signed consent document would be the potential harm resulting from a breach of confidentiality. Rationale/Explanation		The subjects are members of a distinct cultural group or community in which signing forms is not the norm. Rationale/Explanation		There is an appropriate alternative mechanism for documenting that informed consent was obtained. Rationale/Explanation		The research is not FDA-Regulated. Rationale/Explanation		The written script of the information to be provided orally, electronically, or on paper (information sheet) includes all required and appropriate additional elements of consent disclosure. When requesting a waiver of documentation, an information sheet is required. This box should always be checked for a waiver of documentation. (Follow HRP-502I TEMPLATE Information Sheet) Rationale/Explanation		Other Describe any other reasons/explanations for request of waiver/alteration
		N/A not requesting a waiver of documentation of consent.																								
		The research presents no more than minimal risk to subjects. Rationale/Explanation																								
		Written information describing the research is to be provided to the subject, subject parent(s) or guardian(s), or subject Legally Authorized Representative. Rationale/Explanation																								
		Written information describing the research does not need to be provided to the subject, subject parent(s) or guardian(s), or subject Legally Authorized Representative. Rationale/Explanation																								
		The research involves no procedures for which written consent is normally required outside of the research context. Rationale/Explanation																								
		The only record linking the subject and the research would be the consent documentation. Rationale/Explanation																								
		The principal risk of a signed consent document would be the potential harm resulting from a breach of confidentiality. Rationale/Explanation																								
		The subjects are members of a distinct cultural group or community in which signing forms is not the norm. Rationale/Explanation																								
		There is an appropriate alternative mechanism for documenting that informed consent was obtained. Rationale/Explanation																								
		The research is not FDA-Regulated. Rationale/Explanation																								
		The written script of the information to be provided orally, electronically, or on paper (information sheet) includes all required and appropriate additional elements of consent disclosure. When requesting a waiver of documentation, an information sheet is required. This box should always be checked for a waiver of documentation. (Follow HRP-502I TEMPLATE Information Sheet) Rationale/Explanation																								
	Other Describe any other reasons/explanations for request of waiver/alteration																									

